Physical inactivity has been identified as a primary contributor of childhood obesity and related diseases, with underserved youth (minority and low-income status) at greatest risk of inactivity and its health consequences. However, physical activity (PA) interventions have attained limited-to-no sustained behavior change and thus, have rarely affected targeted physiological or anthropometric health outcomes. Despite substantial research noting the importance of social influences and goals (e.g., being with, and making friends) on PA motivation and participation, PA-based interventions have almost exclusively emphasized approaches centered on constructs related to physical ability (e.g., mastery, self-efficacy). To date, little research has focused on understanding the contributions that social goal orientations and need for connectedness make toward promoting sustained youth PA. We argue that during adolescence, when orientation towards social relationships is strongest, the desire for social connections is a primary goal of action underpinning youth PA behavior and thus, a key mechanism to target for sustained behavior change. Thus, the proposed study will address limitations in previous research by targeting the social mechanisms needed within afterschool programs (ASPs) to promote sustained increases in youth PA. Application of social development research, Achievement Goal Theory, and Self-Determination Theory provides the conceptual framework for addressing key social mechanisms: 1) Friendship (and the development of PA-based social skills); 2) Group Belonging (peer connection), and; 3) Connection with ASP Staff. Primary components of the study include “Get to know you” sessions aimed at providing youth guided social opportunities to foster friendship-building skills, and to promote acceptance, cooperation, contribution, and friendship affiliation, and infusing a novel socially-oriented PA curriculum within ASP free play sessions. A total of 8 afterschool programs that serve a primarily underserved population will be asked to participate in the program. During the spring of year 1, (phase 1), staff and youth interviews, youth surveys, and systematic observations of ASP sites were conducted to develop the program curriculum and staff training (previously approved by IRB – **Pro00031648**). During this upcoming Fall of year 1 we plan to test our curriculum during an 8-week pilot (1 intervention and 1 control ASP (N=60 youth). During year 2 (Fall, 2015), after addressing measurement and/or implementation challenges identified in our Y1 pilot, a randomized study (3 intervention and 3 control ASPs) will be implemented to test the feasibility of the intervention approach (N=200 youth). Feasibility of our intervention should demonstrate that intervention youth report greater perceived connectedness and affiliation goal orientation toward PA from baseline to post-intervention. Observations of ASPs will test changes in the social climate from pre- to post-intervention and process evaluation will assess dose and fidelity. It is hypothesized that: 1) youth in the intervention (vs. comparison) will demonstrate greater improvements in positive PA affect, cognitions, and behaviors, and BMI from baseline to post-intervention, and; 2) targeted social mechanisms will mediate the effects of the intervention on changes in PA outcomes.

B. Specific Aims

Physical inactivity has been identified as a primary contributor of childhood obesity and related diseases,¹⁻⁷ with underserved youth (minority and low-income) at greatest risk of inactivity and its health consequences.^{6,7} However, physical activity (PA) interventions have attained limited-to-no sustained behavior change and thus, have rarely affected targeted physiological or anthropometric health outcomes.⁸⁻¹² Extensive research on sport participation shows highly engaged youth report an affiliation orientation towards PA, identifying social reasons and goals (e.g., being with, and making friends) as their primary motivations for participation, and defining PA competence as achieving these social goals.¹³⁻¹⁵ Despite substantial research noting the importance of social goals on PA-based self-determined motivation¹⁶⁻¹⁸ and participation,¹⁹⁻²¹ PA-based interventions have almost exclusively emphasized approaches centered on constructs related to physical ability (e.g., mastery, self-efficacy).²² To date, little research has focused on understanding the contributions that affiliation orientations (social goals) make toward promoting sustained youth PA.^{23,24} We argue that adolescents' desire for social connections is a primary goal of action underpinning their PA behavior and thus, a key mechanism to target for sustained behavior change. The Active by Choice Today (ACT) program, conducted by our investigative team is one of the first afterschool programs (ASPs) to implement a climate-based intervention based on Self-Determination theory which shows significant improvements in PA in underserved youth.²⁵⁻²⁸ However, limited sustained effects found post-intervention, and data from interviews with ACT staff and youth²⁸ which indicated the presence of several interpersonal barriers (e.g., cliques, teasing) to program effectiveness, suggests additional social climate components still need to be addressed. Systematic observations of ASPs using an observational tool that the PI has developed and tested²⁹⁻³¹ and additional interviews conducted with ASP staff and youth further suggests that targeting youth social goals (e.g., building friendships through PA) and social competencies (e.g., friendship-building skills) may be particularly effective for increasing and *sustaining* the PA of underserved youth. Thus, the proposed study aims to test the feasibility of expanding on the social climate approach of ACT to include three key "PA affiliation orientation" elements for increased and sustained youth PA: 1) Friendships (conceptualizing PA success/competence in terms of having close, mutual relationships with other individuals); 2) Group Belonging (defining competence in terms of feeling liked and accepted by peers), and; 3) Staff Acceptance/Connection (viewing success as feeling connected to, supported, and encouraged by staff).¹³⁻¹⁵ These elements have not been explored in prior research and we believe by enhancing ACT to include them in the resultant ACT2-Connect intervention will lead to sustained positive PA affect, cognitions, and behaviors in underserved youth. Comparison of ASPs receiving the 8-week "Connect" intervention (N=3 ASPs) with ASPs randomized to receive the general ASP curriculum (control condition; N=3 ASPs) will yield preliminary data on the effectiveness of social mediators for improving moderate-to-vigorous (MV)PA and preventing obesity among at-risk youth that can inform future intervention design and youth programming policy. Results of this proposed project will provide the basis for conducting a large scale efficacy trial.

Specific Objectives:

Develop and test the feasibility of the "Connect" intervention for increasing PA affect, cognition, and MVPA of underserved youth within ASPs. The effects of the intervention on youth body mass index (BMI) trajectories will also be explored and will have implications for impacting BMI as the targeted outcome of a larger R01 trial.

Primary Aims (Program Development and Feasibility):

1. Through qualitative interviews with staff and youth at ASP sites serving at-risk youth assess:
a) conceptual constructs most relevant for facilitating and supporting youth PA social goals; b)

barriers present within ASPs for meeting PA social goals (addressed in Phase 1, previously approved by IRB: Pro00031648).

2. Explore the feasibility of the Connect program. The Connect program will be documented to be feasible as shown by: 1) youth's greater perceived connectedness and PA affiliation goal orientation from baseline to post-intervention; 2). changes in targeted social climate components from baseline to post-intervention as measured by systematic observations, 3) staff perceptions of feasibility and acceptability of program as measured by a baseline and follow-up readiness assessment, and; 4) adequate dose and fidelity of program implementation as indicated by weekly process evaluations.

Secondary Aims (Document the preliminary impact of the Connect program on PA outcomes):

1. Assess whether youth in the social climate program (vs. comparison) demonstrate greater increases in positive PA affect, cognitions, and MVPA from baseline to 12-weeks post-intervention.
2. Explore whether youth in the social climate program (vs. comparison) demonstrate healthier BMI trajectories (e.g., slight reduction) from baseline to 12-weeks post-intervention.
3. Assess whether changes in targeted social mechanisms will mediate the effects of the intervention on changes in PA affect, cognitions, and MVPA from baseline to post-intervention.

C. Background and Significance

Physical Activity for the Prevention of Obesity and Related Disease

Recognized as the primary health threat for young people, national reports indicate that 34% of youth (40% of African American adolescents) are now considered overweight or obese¹ with minority and low-income youth at greatest risk for obesity and related diseases.^{1,6-7} Sustained levels of moderate-to-vigorous (MV)PA, have been shown to have a strong effect on youth weight status, cardiorespiratory fitness, metabolic health, and body composition.¹⁻⁵ Despite the benefits of PA, 50 - 92% of youth still do not meet national guidelines of 60 minutes of daily PA and PA declines as much as 50% between the elementary and middle school years^{32,33} with greatest declines and lowest levels of PA observed among African American females.³⁴ Efforts to increase PA has become a national priority, however previous PA studies have been unable to sustain behavior change and thus, have rarely affected targeted physiological or anthropometric health outcomes.⁸⁻¹² This may be, in part, because youth intervention approaches have rarely considered youth social developmental needs. We argue that adolescents' desire for social connections is a primary goal of action underpinning their PA behavior and thus, a key mechanism to target for sustained behavior change. **The proposed study will expand on previous research by testing the feasibility of a social-climate intervention within under-resourced afterschool programs (ASPs) that promotes increases in youth daily MVPA through targeting three primary PA social affiliation goals: 1) Friendship, 2) Group Belonging, and 3) Staff Acceptance.**

Need for a Social Climate Approach for Promoting Youth PA

For decades, correlational research within PE and sport settings has shown youth report social reasons and goals (e.g., friendship opportunities, being part of a team, coach behaviors) for initial and continued engagement in PA.¹³⁻²¹ During early adolescence, orientation towards social connections, salience of social feedback, and need for self-preservation within social contexts is more prominent than during any other period of the lifespan.³⁵⁻³⁷ Despite the developmental needs of adolescents, and the theoretical and empirical evidence of the importance of social factors for promoting PA, these factors have been minimally incorporated within intervention design, less well-defined than mastery or autonomy supports, and rarely are

the targeted or primary mechanism for increasing PA. Rather, PA interventions have typically focused on education and behavior modification components (e.g., self-monitoring) as primary mechanisms for promoting sustained PA.³⁸⁻⁵⁰ Some studies have targeted contextual modifications within PA settings (e.g., teacher support, choice of “enjoyable” activities)^{42,48,50-57} however, with an emphasis on promoting PA self-efficacy and skill development rather than socially-relevant goals, they have contributed little to understanding whether these contextual changes affect key PA social mechanisms, and have shown minimal impact on sustained PA behavioral change.¹² Lastly, a small set of studies have been centered on addressing adolescents’ broader PA social experiences,^{52,56,57} with only a single study⁵⁶ linking PA to socially-relevant goals (exploring the importance of dance in African American culture) as a central aim. Although these studies have evidenced some effects on indicators of physical health they have exclusively targeted females and have included minimal measurement of changes in important social mechanisms.

INNOVATION

Expanding on Climate-based PA Interventions for Youth

[figure not shown]
The climate-based approach for our feasibility trial is based on a novel theoretical framework (Figure 1) that expands on the social motivational constructs highlighted by SDT⁵⁸ and Achievement Goal Theory (AGT).⁵⁹ Along with the need for competence and autonomy, SDT highlights the need for positive social interactions for improving long-term life style changes. According to SDT, the basic human need for social connection and meaningful interpersonal relationships should stimulate goal-directed behaviors to satisfy it. However, the social-contextual features needed to meet youth relatedness needs have been less well-defined in previous PA interventions.^{23,60,61} AGT asserts that individuals want to and will strive to display competence in the way they define it,⁵⁹ and that adolescents commonly define PA competence in terms of different social relationships (e.g. peer acceptance, close friendships).¹⁵ However, facilitating and supporting PA orientations that define PA competence in terms of developing positive relationships with others is a key motivational component for sustained PA that has been missing from other PA interventions.

The proposed study addresses the limitations of previous youth PA interventions by targeting youth social goal orientations towards PA as the primary mechanism for promoting PA affect, cognitions, and behaviors in underserved youth. There are two distinct types of social goal orientations towards PA. The first orientation emphasizes affiliation experiences with the opportunity to socialize and develop relationships the primary goals for youth engagement in PA.^{23,24} The second orientation emphasizes social validation and stresses social status and approval from significant others as the primary goals for participating in PA.^{23,24} An affiliation orientation, which has been associated with help seeking, positive affect, and engagement at school, has been shown to be more favorable than a social validation orientation.^{62,63} Previous research has demonstrated three specific components of affiliation orientation that are particularly representative of the types of social relationships important to adolescents within physical domains: 1) Friendships (conceptualizing success/competence in terms of having close, mutual relationships with other individuals); 2) Group Belonging (similar to SDT’s relatedness component, represents youth tendencies to define competence in terms of feeling liked and accepted by a group of peers), and; 3) Staff Acceptance (which tailored to ASPs, can be defined as viewing success as feeling connected to, supported, and encouraged by staff).^{13-15,64} Extensive research on participation motivation in sport, physical education, and exercise shows highly engaged youth and adults report social reasons as their primary motivations for PA participation (viewing PA as an avenue for being with, and making friends, attaining peer acceptance/approval, and feeling connected to a group).^{16-23,65-67} Together, this research suggests that facilitating and supporting an affiliation orientation towards PA during adolescence

may function as a protective factor for sustaining PA throughout adulthood. However, no PA interventions to date have targeted social goal orientations as the key mechanism to promote sustained PA.

The goal of the proposed project is to test the feasibility of a social climate intervention that facilitates and supports PA affiliation goals as the primary mechanism through which youth will improve and sustain their PA affect, cognitions, and behaviors (see Figure 1). Youth focus groups and staff interviews, along with findings of previous research^{13-15,60,61,64} and systematic observations²⁹⁻³¹ were used in phase 1 to identify social climate features needed to facilitate and support youth's key PA affiliation goals: friendship, group belonging, and staff acceptance/connection.

Figure 1. Program Structure and Conceptual Model

D. Research Design and Methods

assessing the PA social-motivational climate of summer camp^{29,30} and ASP³¹ settings conducted by the PI indicated 'positive peer interactions' was a primary predictor of youth higher rates of MVPA [$F(1,329)=8.43$, $p<.01$]. Moreover, findings indicated a clear deficit in observed instances of important social resources for PA (e.g., < 3% observed instances of staff verbal praise or PA promotion; 20% of activities were inclusive; 11% involved staff PA participation; 14% involved positive peer interactions).²⁹⁻³¹ The PI also conducted interviews and focus groups with 7 of the ASP sites (26 staff, 102 youth) to identify an initial set of social motivators and barriers for youth PA within each site and the program's "readiness" for implementing the proposed intervention. Findings indicated the majority of staff (84%) view PA as a primary mission of their ASP (Freq=36; 24 staff; 6 programs), but also report several socially-based challenges to get youth active including "cliques, peer pressure, social norms" (freq=10; 7 staff; 4 programs) and youth "poor PA self-concept" (e.g., self-conscious, shy, afraid to mess up; Freq=9; 8 staff; 5 programs). Further, "finding better ways to motivate youth to participate with peers in PA" (5 staff; 4 programs) emerged as a common theme when staff were asked about ways to improve the program. These findings contribute to our understanding of the strengths and needs of ASPs, and the key mechanisms for inducing youth PA behavior change that will inform the proposed intervention design.

Study Design of Proposed Connectedness Feasibility Trial

The proposed project will be a prospective, randomized controlled trial comparing a social climate program to a general ASP.

The proposed project will be implemented over a 2 year period (see Figure 2). A planning phase occurred during the first six months in order to conduct staff interviews, youth focus groups, and systematic observations of each ASP, hire staff, pilot survey measures, and revise intervention materials and evaluation tools based on observations, surveys, and interview and focus group feedback (addressed in phase 1 IRB application). During the fall of year 1, an 8-week pilot will be tested in 1 ASP (N=30) and compared to a general health curriculum school-based control (N=30). Results of the pilot study will be used to inform any necessary modifications of the intervention approach or measurement protocol for year 2.

During year 2, a randomized study (3 intervention and 3 control ASPs) will be implemented to test the feasibility of the intervention approach (N=200 youth). A 12-week follow-up, will test the sustained effects of the social climate intervention on ASP PA climate, youth PA affect, cognitions, behaviors, and BMI

Figure 2. Project Timeline

YEAR 1	YEAR 2
April-Sept 2014 - Interviews/Focus Groups - Observations - Intervention development - ASP program recruitment - Hire and Train Staff	Aug-Oct 2015 - Intervention/Measurement Staff Training - Baseline Data Collection (2 ASPs) - Intervention Implement cohort 1
Sept-Dec 2014 - Pilot Baseline Data Collection - Pilot Intervention (1 ASP vs. 1 control)	Oct-Dec 2015 - Baseline Data Collection for cohort 2 (2 more ASPs) - Intervention Implement (cohort 2)
Feb-Apr 2015 - Post-measures in Pilot ASPs - Data cleaning - Hire Project Staff for Y2	Jan-March 2016 - Post-measures for cohorts 1 and 2 - Baseline data collection for cohort 3 (2 ASPs) - Intervention implement (Cohort 3)
April-July 2015 -Data analysis - Revisions to intervention and measurement - ASP Recruitment for Y2	April-May 2016 - Post-measures cohort 3 - Data Management/ Analysis -Manuscript Preparation

Primary Aim 1 (COMPLETED PHASE 1): Interviews/Focus Groups and Youth Survey

Measures. During year 1, we conducted staff interviews (SIs) and youth focus groups (FGs; youth ages 9-14) in ASP sites to assess 1) key physical (e.g., equipment allocation), structural (e.g., PA preferences, activities offered), interpersonal (e.g., peer behaviors), and intrapersonal supports (e.g., social skills) needed to promote and support a social affiliation orientation towards PA (friendship, group belonging, and staff connection goals), 2) program barriers impeding the development and achievement of these social goals, and 3) input on the design and feasibility of initially- developed program components. Through content analysis (NVivo) we identified key themes related to improving social affiliation that were used to inform the development and implementation of the social climate intervention.

Targeted Population, Recruitment, and Retention. We aim to recruit 8 middle-school ASPs located within a 70 mile radius of Columbia that serve a primarily underserved population of middle school youth (6th-8th grade) youth. All ASP sites will need to include 1 hour of daily PA/freeplay as one component of the curriculum and be similar in size, percentage of youth per site on free or reduced lunch, race, and gender. One ASP will be asked to participate in the pilot during year 1 and will be compared to a school-based control (youth in the control will receive our general health curriculum administered in their health class during the school day). During year 2, six ASPs will be randomized to the treatment or control (general health curriculum) conditions after baseline data collection. ASP staff and all youth enrolled in the program will be asked to participate in the study. To be eligible, youth must 1) be enrolled in the ASP, 2) have parental consent and assent to participate, and 3) be available for baseline and post-intervention measurement. Youth will be excluded from participation only if they have a medical condition that would interfere with the program's prescribed PA.

Overview of Intervention.

Drawing from theory and previous correlational^{13-21,64-72} and qualitative research,^{60,61} along with our preliminary studies in ASPs²⁵⁻³¹ we have identified key components for establishing a positive PA social climate that will inform the initial development of the intervention (see **Appendix A**). The intervention will target multiple levels of the ASP setting including staff- and peer- behaviors, program structure (e.g., activities), and the physical environment. Initial essential elements were derived from common themes identified across these levels including: 1) moral, emotional, and social goal-oriented support and skill development (e.g., friendship-building skills) 2) collaborative, cooperative play centered on friendship and informal-fun; 3) equal treatment and access, and; 4) inclusive and engaging for both youth and staff. The primary components of the study include: 1) "Get to know you" sessions aimed specifically at providing youth guided social opportunities to foster friendship building skills, and to promote acceptance, cooperation, contribution (to self and others), and friendship affiliation, and; 2) infusing a novel socially-oriented PA curriculum within ASPs' free play sessions (see **Appendix B**). The intervention will take place during ASPs' 1.5 hour "free play" component 2 times per week for 8 weeks. **[name] (Consultant), [name] (co-I)**, and a staff of **Physical Educators** will assist the **PI** in designing all program activities to meet the criteria of the essential elements.

The "Get to Know You" small group sessions (30 minutes) will be designed to specifically increase friendship building skills, and a value and efficacy for contributing to the health and well-being of oneself and others. It will involve interactive student-led discussions and activities that are designed to foster the intra- and interpersonal assets needed to build and support friendships, group cohesion, and staff connections through PA. For example, in small (staff-assigned) groups, staff will challenge youth with fun team building activities and icebreakers, youth will be encouraged to share ideas (e.g., brainstorm sessions on best methods for teaching friends new activities; how to be a good friend, active listener), personal stories, preferences,

and goals (e.g., their happiest/scariest memory, favorite PA to do with a friend), and activities (e.g., they will each be asked to bring in a favorite activity to teach their peers). They will also collaborate each program day to develop a campaign to encourage others to be active (e.g., family members, friends, teachers). This will include developing fliers/posters, and logos, performing and recording an entertaining media/video clip, and designing their own choreography for a dance or martial arts routine that they will teach and then perform with their targeted group (families, friends, teachers) at a ‘family and friends’ night, to further empower youth to exercise their newly developed PA-based social skills and goals, build social connections through PA outside of ASP time, and help sustain PA behaviors post-intervention. (See Appendix C for “Get-To-Know You” curriculum)

The PA component (60 minutes). Youth will participate in one of three socially-oriented physical activities that will be offered based on student preference ratings obtained the week prior. Studies by our group²⁵⁻²⁸ show that student motivation is increased by allowing students to vote for their PA preferences among a list of activities. To promote a PA affiliation orientation, available games to choose from will be novel, inclusive, emphasize teamwork, and centered on social goals that involve components of the “get to know you” sessions. (See Appendix D for PA curriculum)

The Comprehensive (general) Health Comparison Program (60minutes). (See Appendix E for comprehensive health curriculum). The comparison programs (ie., during health class for year 1 pilot; 3 ASP in year 2) will receive a comprehensive health curriculum within their programs that is designed to increase youth knowledge and skills across a wide variety of health-based behaviors. The curriculum includes interactive components addressing stress management and reduction (yoga and breathing exercises), media literacy and cyber safety, self-discipline (achievement and goal setting, martial arts), risk prevention, and building a positive self-esteem and positive thinking.

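### Year-2 programs enter in three calendar pairs with no stated within-pair randomisation rule, and Figure 2 is too short for cohort 3's 12-week follow-up

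*Combined protocol and SAP*

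**What the plan says.** **Allocation.** In section D, Targeted Population, Recruitment, and Retention, the year-2 rule is that "six ASPs will be randomized to the treatment or control (general health curriculum) conditions after baseline data collection". The Study Design section fixes the totals: "a randomized study (3 intervention and 3 control ASPs) will be implemented to test the feasibility". No section describes how 3:3 is reached, and none mentions pairing, blocking or stratifying by cohort. The requirement that sites resemble each other in size and make-up governs which sites are recruited, not how they are allocated.

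**Calendar.** Figure 2 is the only dated schedule. For year 2 it lists:

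- "Aug-Oct 2015 - Intervention/Measurement Staff Training - Baseline Data Collection (2 ASPs) - Intervention Implement cohort 1"
- in Oct-Dec 2015, "Baseline Data Collection for cohort 2 (2 more ASPs) - Intervention Implement (cohort 2"
- in Jan-March 2016, "Post-measures for cohorts 1 and 2 - Baseline data collection for cohort 3 (2 ASPs) - Intervention implement (Cohort 3"
- "April-May 2016 - Post-measures cohort 3"

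**Waves.** Secondary Aim 1 asks whether intervention youth "demonstrate greater increases in positive PA affect, cognitions, and MVPA from baseline to 12-weeks post-intervention". The Study Design section adds: "A 12-week follow-up, will test the sustained effects of the social climate intervention". The accelerometer paragraph calls for seven days of wear on three occasions: before the program, at its end, and later. The Primary Aim 2 model likewise has two post-baseline points. The program lasts 8 weeks (Overview of Intervention).

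**Model.** The Analysis Plan adjusts for demographics, BMI (at baseline under Primary Aim 2; for the PA outcomes under the Secondary Aims), and whatever is found to differ between arms at baseline. It names no cohort or season term.

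**The concern.** Cohort 1 starts its program before cohort 3 has a baseline, so randomisation after baseline cannot be a single draw with all six baselines in hand. If the stepwise draw happens to put both ASPs of a cohort in the same arm, any change that differs between calendar periods, from late summer to spring, is mixed into the arm contrast. Adding a cohort term afterwards is a weak repair, because the effect then rests on the one split cohort, 1 ASP against 1 ASP.

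The second issue is whether the dated schedule can deliver the 12-week measurement that the aims promise for the last pair. The Analysis Plan uses this study to gauge an effect size for a larger trial, and the sustained effect is central to its rationale. An estimate that pools unlabelled and unequal follow-up intervals is hard to carry forward.

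**Working it through.** **Reproducing the plan's count.** Figure 2 gives 2 + 2 + 2 = 6 ASPs, which matches 3 + 3 = 6 in the Study Design section.

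**Allocation.** The inputs are six ASPs, three cohorts of two, and 3:3 overall. Assume first that 3:3 is drawn with no cohort restriction.

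- Possible allocations: C(6,3) = 20.
- One ASP per arm in every cohort: 2 × 2 × 2 = 8, or 8/20 = 40%.
- The remaining 20 − 8 = 12 (60%) each have one cohort wholly in intervention, another wholly in control, and the third split. Check: 3 × 2 = 6 ordered choices of the two unsplit cohorts, times 2 ways to split the third, gives 12.

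For the effect on the contrast, take ASPs of equal size and let a, b and c be the mean changes due to calendar period alone. Let cohort A be wholly intervention, B wholly control, and C split:

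- intervention mean = (2a + c)/3
- control mean = (2b + c)/3
- difference = (2/3)(a − b)

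Over all 20 draws, the coefficient of any one cohort is −2/3, 0 or +2/3 with frequencies 4, 12 and 4, so its mean is 0. The documents give no value for a − b.

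With one ASP per arm in each cohort, there are 2³ = 8 allocations, all are 3:3, and none leaves a cohort unsplit. The smallest two-sided site-level randomisation p is 2/8 = 0.25, against 2/20 = 0.10 without the restriction.

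**Cohort 3 calendar.** The month boxes are read as generously as possible, from the first day to the last with no breaks. The 12 weeks run from the end of the program, as Secondary Aim 1 words it.

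- Available, 1 January to 31 May 2016: 31 + 29 + 31 + 30 + 31 = 152 days.

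| Components | Days | Margin against 152 |
|---|---|---|
| Baseline wear 7 + program 56 + 12 weeks 84 | 147 | 5 spare |
| The same + follow-up wear 7 | 154 | 2 short (ends 2 June) |

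Starting on Monday 4 January instead, the margins are 2 days spare and 5 days short. Without follow-up wear, the program must end by 31 May − 84 days = 8 March. Figure 2 lets it run to 31 March, and 31 March + 84 days = 23 June.

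**Cohorts 1 and 2.** Their post-measures box is Jan-March 2016.

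- Cohort 1: programs ending from 9 to 31 October reach week 12 between 1 and 23 January.
- Cohort 2: with 7 + 56 days from 1 October, the earliest program end is 2 December. Ends from 2 to 31 December reach week 12 between 24 February and 24 March.

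The box therefore suits a 12-week wave for both cohorts, apart from a cohort 1 program finishing before 9 October.

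**The case against.** **Allocation.** Three successive pairs that reach 3:3 suggest that one ASP per arm in each pair was always meant. If so, the chance of an unsplit cohort is 0%, not 60%. That stands as a plausible reading, which is why the 60% is conditional and the finding is an omission. The adjustment clause for baseline differences could admit a cohort term, but only after an imbalance has occurred.

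**Waves.** A reader might infer from the single post-measure entry per cohort that the end-of-program wave was dropped, or that cohort 1 goes unmeasured until January 2016. The documents do not support this. In both the accelerometer paragraph and the Primary Aim 2 model, post-intervention is the later wave, and the Jan-March 2016 box falls where week 12 would fall. The end-of-program wave is required elsewhere and simply not itemised in a month-level project timeline. Nor does Figure 2 show that cohort 3 cannot have both waves: an end-of-program measurement could be taken in March.

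**Follow-up wear.** If the seven days of wear were completed by week 12, 147 days would be enough. The plan states no such convention, and the margin would still be 5 days at best, with nothing set aside for randomising between baseline and program start.

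**Foreknowledge.** A reader might also infer that the last pair's assignment could be deduced from earlier draws and so bias recruitment or measurement. No route for that is shown: year-2 sites are recruited in April-July 2015, all enrolled youth are invited, and measurement staff are blind to assignment.

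**Conclusion.** Both parts hold, at different strengths.

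**Allocation** is an omission with a cheap remedy. The plan does not state a within-cohort rule that its own stepwise calendar calls for. Under an unrestricted 3:3 draw, 12 of 20 allocations confound two cohorts with arm and pass 2/3 of their difference in change into the contrast, assuming equal ASP sizes. A reader might conclude that the trial is confounded or its estimate biased. That goes too far: the effect is conditional on the draw and zero on average over draws, and its size in outcome units is unknown.

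**Timing** is wrong as written, for cohort 3 only. On the most generous reading the full sequence needs 154 days and Figure 2 offers 152. Without follow-up wear it fits only if the program ends by 8 March. This rests on counting 12 weeks from program end; counted from baseline, cohort 3 would fit easily, but Secondary Aim 1 is not worded that way.

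The change should be made, but for a feasibility study it does not undermine the design.

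**What to change.** 1. In Targeted Population, Recruitment, and Retention, state that once both ASPs of a cohort have completed baseline, one is randomised to each arm within that cohort. This guarantees 3:3 and splits every cohort.
2. In the Analysis Plan, add a cohort-by-time adjusted version of the repeated measures models as a supportive analysis.
3. Reconcile Figure 2 with the Secondary Aims, the Study Design section, the accelerometer paragraph and the Primary Aim 2 model by showing the end-of-program and 12-week waves separately for each cohort.
4. For cohort 3, either extend the measurement window or label the April-May data by the interval actually achieved. In either case, report the actual follow-up interval for each ASP.

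**Cost.** Item 1 is one sentence, but it cuts the allocations from 20 to 8 and raises the smallest two-sided site-level randomisation p from 0.10 to 0.25. That limits a site-level randomisation test only; it does not affect the planned youth-level ANCOVA. Extending cohort 3 could mean measuring as late as 23 June or beyond, and the documents do not say whether ASPs still meet then. If cohort 3 is instead labelled as a shorter follow-up, the 12-week contrast rests on the four ASPs of cohorts 1 and 2.
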